# 10.2 Statistical Hypotheses

The null hypothesis for the primary endpoint is that there is no difference in the ORR of the Nivolumab and BMS-986253 combination and the ORR of the Nivolumab monotherapy.

The null hypothesis for the secondary endpoint is that there is no difference in TTR, DOR, PFS, OS, and safety for the Nivolumab and BMS-986253 combination and the Nivolumab monotherapy arm.

The alternative hypothesis for the primary endpoint is that there is a difference in the ORR of the Nivolumab and BMS-986253 combination and the ORR of the Nivolumab monotherapy.

The alternative hypothesis for the secondary endpoint is that there is a difference in TTR, DOR, PFS, OS, and safety for the Nivolumab and BMS-986253 combination and the Nivolumab monotherapy arm.

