## 10.4 Description of Statistical Methods

#### 10.4.1 General Approach

Descriptive statistics will be provided for every covariate and outcome by the studied arms. Continuous data will be presented as means with standard deviations, and categorical data will be presented as numbers with percentages. All p-values will be two sided. Normality assumptions will be checked and log transformation will be considered if normality assumption is violated.

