#### 10.4.2 Analysis of the Primary Efficacy Endpoint(s)

ORR will be defined as the best objective response using RECIST v.1.1 criteria based on MRI or CT scan evaluations following treatment. ORR will be compared by two-sample proportion test between BMS-986253 in combination with Nivolumab in comparison to Nivolumab monotherapy. P-values will be two-sided and any p-values less than 0.05 will be significant. No adjustment to significance determination for multiple comparisons will be made.

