#### 10.4.3 Analysis of the Secondary Endpoint(s)

Secondary Endpoints, including TTR, DOR, PFS, OS, and exploratory analysis of the HCC TME, will be performed. TTR and DOR will be described and PFS and OS will be compared between subjects receiving BMS-986253 in combination with Nivolumab in comparison to Nivolumab monotherapy. Kaplan-Meier method will be used to analyze the median TTR, DOR, PFS, and OS. Categorical variables will be compared by two-sample proportion test, survival outcomes will be compared by log rank test, and continuous outcome will be compared by two-sample t-test.

Version: 11.0

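### The plan's only significance rule is not confined to ORR, and nothing labels the PFS and OS p-values as nominal

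*Combined protocol and SAP*

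**What the plan says.** Section 10.2 gives ORR its own hypothesis ("The null hypothesis for the primary endpoint is that there is no difference in the ORR") and then a single secondary one: "The null hypothesis for the secondary endpoint is that there is no difference in TTR, DOR, PFS, OS, and safety". The matching alternative names the same list of endpoints.

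Section 10.4.2, under the primary efficacy endpoint, holds the only significance rule in Section 10: "P-values will be two-sided and any p-values less than 0.05 will be significant". The next sentence is: "No adjustment to significance determination for multiple comparisons will be made".

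Section 10.4.3 leaves TTR and DOR as descriptive, but "PFS and OS will be compared between subjects receiving BMS-986253 in combination with Nivolumab in comparison to Nivolumab monotherapy", using the log-rank test. It gives no threshold of its own.

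ORR is ranked above PFS and OS throughout (protocol summary, Sections 3.1, 3.2, 4.2.1 and 4.2.2), and Section 10.5 bases the sample size on ORR alone. Nowhere is there a testing order, a division of alpha, or a statement that the PFS and OS p-values are nominal. Section 10.1 defers a formal SAP to a date before database lock.

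**The concern.** Three efficacy comparisons (ORR, PFS and OS) carry a stated hypothesis and a named test, and the one rule available says that "any p-values less than 0.05 will be significant". After a missed ORR, the text would allow a PFS or OS difference to be reported as significant at the full 0.05, with no statement that it does not count as evidence of efficacy.

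A missed ORR is a realistic outcome, because Section 10.5 powers the trial only for a 34-point difference. Two later decisions also turn on the reading of efficacy without naming an endpoint: expanding the cohort if results look promising (Section 10.5), and continued access to drug if one arm is shown to be superior (Section 7.8).

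**Working it through.** **Inputs from the documents.** 25 per arm, ORR 15% against 49%, two-sided 0.05, Z-test without pooling of variances (Section 10.5); all randomised participants (Section 10.3); ORR, PFS and OS compared, TTR and DOR only described (Sections 10.4.2 and 10.4.3).

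**Input not in the documents.** The correlation between the three test statistics. Assumed 0 to 0.8.

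**1. The plan's own figure.** SE = √(0.15×0.85/25 + 0.49×0.51/25) = √(0.00510 + 0.00999) = 0.1229. Power = Φ(0.34/0.1229 − 1.96) = Φ(0.807) = 79.0%; exact binomial enumeration gives 79.1%. The stated 80% is reproduced to within rounding. With 15% in both arms, the exact size of this test is 5.5%. The ORR test therefore does what Section 10.5 says.

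**2. Three tests, no treatment effect, independence.** At least one significant in either direction: 1 − 0.95³ = 14.3%. At least one favouring the combination: 1 − 0.975³ = 7.3%.

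**3. Three correlated tests.** Trivariate normal simulation, 1,000,000 draws per setting:

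| Common correlation | Any of three, either direction | Any of three, favouring combination | PFS or OS alone, either direction |
|---|---|---|---|
| 0 | 14.3% | 7.3% | 9.8% |
| 0.3 | 13.7% | 6.8% | 9.5% |
| 0.5 | 12.5% | 6.2% | 9.0% |
| 0.8 | 9.9% | 4.9% | 7.9% |

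Against a single test (5% in either direction, 2.5% in one), the multiple runs from 9.9/5 = 2.0 to 14.3/5 = 2.9.

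**4. Patient-level check.** 20,000 simulated null trials with 25 per arm. From Section 2.2.2: 15% response, 42% stable disease, and median OS of 16.7 months (stable) and 8.9 months (progressive). Assumed: median OS of 60 months in responders; median PFS of 24, 6 and 1.9 months for response, stable and progressive disease; censoring uniform over 12 to 36 months. The correlations came out at 0.55 (ORR and PFS), 0.36 (ORR and OS) and 0.47 (PFS and OS). At least one significant result occurred in 13.7% of trials, and at least one favouring the combination in 6.8%. Each single test rejected in about 5.4% of trials, slightly above nominal, which is why 13.7% exceeds the 12.7% that the normal model gives at these correlations.

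**5. Which reading of Section 10.4.2?** The two sentences sit under the primary endpoint. With two arms and one ORR comparison, a sentence about multiple comparisons has almost nothing to act on unless it reaches other endpoints. If it does cover ORR alone, PFS and OS have hypotheses and tests but no rule for interpreting them, and the same clarification is needed.

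**The case against.** The strongest case on the other side is that this is an openly declared choice in a 50-patient phase II trial with a clear primary endpoint. A reader told that nothing was adjusted, and shown a secondary endpoint, can discount it. Section 10.5 is about seeking a signal: estimate effects with intervals if significance is missed, and perhaps expand if promising. The SAP still to come may settle the labelling. All of this stands, and it makes the point a matter of interpretation rather than a fault in the design. It does not settle it, because the current text calls such p-values significant instead of nominal.

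Four stronger readings are tempting, but the documents do not support them:

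- *The trial's stated 5% error rate becomes 13%.* Section 10.5 attaches 0.05 to the ORR test only, and that test keeps its size. The plan states no trial-wide error rate.
- *There is no hierarchy.* ORR is ranked primary throughout. What is missing is a testing order or a label.
- *One significant secondary endpoint would reject the secondary hypothesis.* Section 10.2 lists several endpoints in one statement but gives no rejection rule.
- *Five efficacy tests inflate the rate to 22.6% (1 − 0.95⁵).* Section 10.4.3 only describes TTR and DOR.

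Whether small phase II trials need formal gatekeeping of secondary endpoints without a power calculation is debatable, and the point does not depend on it.

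**Conclusion.** The point holds as a cheap improvement, not as an error in a stated figure. If the rule in Section 10.4.2 covers PFS and OS, an inactive add-on gives about a 10% to 14% chance of at least one result called significant. The part that would mislead in favour of the combination is about 5% to 7%, against 2.5% for one test.

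These figures rest on two things: reading the rule across endpoints, which is more natural but not explicit, and the assumed correlation of 0 to 0.8. The patient-level result near the upper end also depends on assumed PFS medians, responder survival and censoring.

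**What to change.** In Section 10.4.2, replace both sentences, the one on p-values below 0.05 and the one on non-adjustment. Replacing only the second would leave a rule that contradicts the new text. Suggested wording:

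*The ORR comparison in all randomised participants is the only test of efficacy, at two-sided 0.05. P-values for all other endpoints, including PFS, OS, safety and TME markers, are nominal, not adjusted for multiplicity, and support no claim of significance.*

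In Section 10.2, limit the formal efficacy hypotheses to ORR. Carry the same wording into the SAP before database lock.

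A false efficacy claim can then arise only from the ORR test, at its nominal 5%. The cost is a few sentences. No patients or data are added, and the ORR test and its power are unchanged. The downside is that a PFS or OS p-value below 0.05 could not be called significant, even after a positive ORR.

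If the investigators want to keep that possibility, a fixed sequence of ORR, then PFS, then OS, each at two-sided 0.05 and stopping at the first non-significant result, also holds the nominal 5%. This is optional, and it would give formal status to two endpoints for which the plan has no power calculation.

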#### 10.4.3 Analysis of the Secondary Endpoint(s)

Secondary Endpoints, including TTR, DOR, PFS, OS, and exploratory analysis of the HCC TME, will be performed. TTR and DOR will be described and PFS and OS will be compared between subjects receiving BMS-986253 in combination with Nivolumab in comparison to Nivolumab monotherapy. Kaplan-Meier method will be used to analyze the median TTR, DOR, PFS, and OS. Categorical variables will be compared by two-sample proportion test, survival outcomes will be compared by log rank test, and continuous outcome will be compared by two-sample t-test.

Version: 11.0

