In order to maximize the potential response to immunotherapeutics, other targeting strategies in the TME should be investigated. TAMs and myeloid-derived suppressive cells (MDSCs) are the dominant immune suppressive cells within the TME (8). In HCC, TAMs have been directly linked to a worse prognosis (9, 10) and TAMs often reside at the invasive front of malignancies (11). We and others have shown that TAMs and their secreted factors, particularly IL-6 and IL-8, contribute to HCC CSC and EMT phenotype (12, 13) (Fig. 1-2, Appendix). Additionally, IL-6 and M-CSF are both known to contribute to monocyte differentiation into TAMs (14, 15). IL-8 has been independently linked to poor prognosis, being important for tumor angiogenesis. Indeed, we have shown that serum levels of IL-8 independently predicted worse survival in a cohort of HCC patients (16) (Fig. 3, Appendix). Additionally, a recent pan-tumor study in patients receiving nivolumab based therapy showed that patients with increased baseline IL-8 had worse overall survival and less responsiveness to nivolumab therapy (ASCO Meeting, 2018). Furthermore, we have shown that IL-6 and IL-8 are dominant cytokines released from TAMs in HCC (Fig. 4, Appendix). These cytokines are responsible for stimulating cancer stem cell (CSC) function as well as epithelial-mesenchymal transition (EMT) behavior (**Fig. 5-6**, Appendix). *Therefore, our overall hypothesis is that therapeutic agents* directed at targeting the function of TAMs may provide additive or synergistic benefits to known checkpoint inhibitor drugs such as Nivolumab.

With these aims toward disrupting TAM function in cancer for therapeutic effect, recent studies to verify dose and safety have been utilized for BMS-986253, an antibody to IL-8. A dose of BMS-986253 at 4 mg/kg up to 32 mg/kg IV every two weeks as monotherapy was found to be safe. Additionally, the combination of BMS-986253 (variant doses every 2-4 weeks) and Nivolumab (480 mg IV every 4 weeks) was found to be tolerable. Therefore in order to target TAM function in HCC more effectively, we will compare combination therapy of Nivolumab and BMS-986253 to Nivolumab monotherapy and evaluated for improved ORR along with other biologic correlates.

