#### 7.2.2 Other Assays or Procedures

Serum IL-8 determination: Venipuncture for blood into yellow top tube (2-3 mL) to collect blood/serum for IL-8 at screening and at beginning of cycle 4. Serum will be collected on site, frozen, and sent on dry ice for screening IL-8 assay at Rules Based Medicine. IL-8 assay will be performed using the Luminex

Version: 11.0

ELISA so that screening IL-8 level can be determined. Serum obtained may be saved frozen (-20°C) in aliquots for later exploratory analysis.

Pre- (Standard of Care) and On-treatment (Translational/Correlative Study) Tumor Core Biopsies: Ultrasound guided or CT guided percutaneous core needle biopsies will be performed by Interventional Radiology. Core needle biopsies (6 cores) will be obtained using 14-18G needles as per Standard of Care techniques for both pre-treatment and on-treatment biopsies. Fresh cores (4 pre-treatment and 6 on-treatment) will be placed immediately in Miltenyi Tissue Storage Buffer on ice. Two cores (pre-treatment only) will go to pathology for SOC evaluation. Research samples will then be processed and analyzed at NYU ([name] Lab).

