# 10.5 Sample Size

Group sample sizes of 25 in Nivolumab combination group and 25 in Nivolumab-only monotherapy group achieve 80% power to detect a difference between the group ORRs of 34%. The ORR in Nivo-only group is assumed to be 15%. The ORR in Nivolumab combination group is assumed to be 49% under the alternative hypothesis. The test statistic used is the two-sided Z-Test with unpooled variance. The significance level of the test is 0.05.

The powered sample size and expected ORR is based upon results from the phase II study of nivolumab in HCC as well as other checkpoint inhibitors (e.g. pembrolizumab) in HCC. If the results do not show significant efficacy, the HRs and 95% CIs will be estimated to quantify the magnitude of the efficacy in each treatment arm. If results are sufficiently promising, then the protocol may be amended to expand the cohort to allow comparison between treatments with higher confidence.

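### Screening IL-8, which the protocol calls prognostic, enters none of the planned ORR, PFS or OS comparisons; an IL-8-adjusted Cox model should be pre-specified before database lock

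*Combined protocol and SAP*

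**What the plan says.** BMS-986253 is an antibody to IL-8 (section 2.2). Section 2.3 reports that "serum levels of IL-8 independently predicted worse survival in a cohort of HCC patients", and that in a pan-tumour study of nivolumab-based therapy "patients with increased baseline IL-8 had worse overall survival and less responsiveness to nivolumab therapy". Nivolumab is given in both arms.

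Blood for IL-8 is taken at the screening visit (section 7.3.1, and the translational blood sample in section 20). Section 7.2.2 says the assay is done "so that screening IL-8 level can be determined", but names no analysis that uses the value. Section 7.2.4 allows screening sera to be frozen and assayed later in batches.

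The planned comparisons do not use it. Section 10.4.2: "ORR will be compared by two-sample proportion test between BMS-986253 in combination with Nivolumab in comparison to Nivolumab monotherapy". Section 10.4.3: "survival outcomes will be compared by log rank test". Neither names a covariate or stratum. Section 10.6 stratifies randomisation by centre only. Section 10.4.1 promises descriptive summaries of covariates by arm. Section 10.5 promises HRs with 95% confidence intervals if efficacy is not significant, without naming a model. Section 10.1 defers a formal SAP to before database lock.

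**The concern.** The protocol itself names one baseline variable as related to survival and to response on the backbone drug. That variable is also the target of the added drug. Leaving it out of the survival comparison can cost power and moves the marginal HR towards 1. With 25 per arm, some chance imbalance in IL-8 is also likely.

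Timing matters too. Section 10.5 leaves the HR model open and allows the cohort to be expanded if results are promising. Section 8.10 has the monitoring committee assess efficacy by arm each quarter, and section 6.1.2 lists both drugs as open label. An IL-8 model chosen after results are known would be open to the charge of selection. One fixed beforehand would not.

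**Working it through.** **1. The plan's own power figure.** Section 10.5 gives 25 per arm, ORR 15% versus 49%, "The test statistic used is the two-sided Z-Test with unpooled variance" and "The significance level of the test is 0.05".

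SE = √(0.15×0.85/25 + 0.49×0.51/25) = √(0.005100 + 0.009996) = 0.1229.
Power = Φ(0.34/0.1229 − 1.96) = Φ(0.807) = 79.0%.

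This reproduces the stated 80% to within rounding. It is the only power figure; none is given for PFS, OS or any IL-8 analysis.

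**2. Survival comparison: planned log rank against IL-8-adjusted Cox.** The following are assumptions and are not in the documents: exponential times, control median 12 months, conditional treatment HR 0.5, censoring uniform over 12 to 30 months, and log IL-8 standard normal and log-linear in the hazard. For scale, section 2.2.2 cites median OS of 8.9 months (progressive disease) and 16.7 months (stable disease) on nivolumab.

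Expected events with inert IL-8:
- Control, probability censored: (12/ln 2)/18 × (2^−1 − 2^−2.5) = 0.962 × 0.323 = 0.311, so 25 × 0.689 = 17.2 events.
- Combination (median 24 months): (24/ln 2)/18 × (2^−0.5 − 2^−1.25) = 1.924 × 0.287 = 0.551, so 25 × 0.449 = 11.2 events.
- Total about 28.4.

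Schoenfeld's formula then gives Φ(ln 2 × √28.4/2 − 1.96) = Φ(−0.113) = 45.5%, in line with the simulated 44% below.

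Simulated power in two separate runs (the first of 4,000 trials per setting):

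| IL-8 HR per SD | Log rank | Adjusted Cox | Difference (points) |
|---|---|---|---|
| 1.0 (inert) | 44%; 44% | 41%; 42% | −3; −2 |
| 1.5 | 40%; 41% | 42%; 43% | +2; +2 |
| 2.0 | 34%; 36% | 43%; 43% | +9; +7 |

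Type I error of the log rank is about 5%.

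*Sensitivity to events.* With 40 events assumed, the power of log rank against adjusted Cox is 56.3% v 58.4% at an IL-8 HR of 1.3 per SD, 48.1% v 55.8% at 1.6, and 42.3% v 56.6% at 2.0. The pattern is the same, with a larger gain for a strong covariate when there are more events.

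*Size of the estimate.* In a separate simulation of 1,500 trials at 2.0 per SD, the average HR was 0.54 unadjusted and 0.48 adjusted, against a conditional truth of 0.5.

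**3. Chance imbalance.** Split IL-8 at the pooled median, 25 high and 25 low. If X of the 25 in one arm are high, X is hypergeometric(50, 25, 25) and the arms differ by |2X − 25|/25.
- At least 20 points (X ≤ 10 or X ≥ 15): 26%.
- At least 12 points (X ≤ 11 or X ≥ 14): 57%.

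Effect on ORR = imbalance × (low-IL-8 rate − high-IL-8 rate), using assumed control rates. For 20% v 10%, 0.20 × 10 = 2.0 points. For 24% v 6%, 0.20 × 18 = 3.6 points. The SE of the ORR difference is 12.3 points (step 1).

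**4. Treatment-by-IL-8 interaction at an assumed 40 events.** SE of the log ratio of HRs = √(16/40) = 0.632.
- 2-fold ratio: Φ(0.693/0.632 − 1.96) = 19%.
- 3-fold ratio: Φ(1.099/0.632 − 1.96) = 41%.
- For 80% power the ratio must be about 5.9-fold.

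**The case against.** *PFS and OS are unpowered secondary endpoints.* True. At 40 events, 80% power needs a treatment HR of exp(−2 × 2.802/√40) = 0.41, so sample size limits these comparisons more than the missing covariate does.

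*The gain may be nil.* This also stands. It is material only for a strong IL-8 effect, which the documents do not quantify. A reader might infer that the PFS and OS contrasts lose power outright; the table does not support that.

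*Imbalance is already part of randomisation error.* Correct. A reader might infer that imbalance invalidates the comparisons. It does not: type I error stays near 5%, and an ORR shift of 2 to 3.6 points is small beside an SE of 12.3. The gap between 0.54 and 0.48 is largely the difference between a marginal and a conditional effect, and 0.48 is itself slightly below the true 0.5.

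*An IL-8 analysis may be planned elsewhere.* The Protocol Summary's sentence on translational endpoints is cut off in the copy reviewed, section 7.2.2 mentions later exploratory use of serum, and section 4.2.3 plans a biomarker search in biopsies. So it cannot be said that no IL-8 analysis of any kind is planned. Sections 10.4.2 and 10.4.3 are complete, however, and the comparisons they state do not use IL-8.

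*The SAP is still to be written.* That is why the change is cheap. It does not supply the model.

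**Conclusion.** The point holds as a matter of efficiency and pre-specification. A baseline value that the protocol calls prognostic is collected before treatment and used in no planned efficacy comparison or randomisation stratum. Against the planned log rank, adjustment changes power by about −2 points if IL-8 is inert, +2 at an HR of 1.5 per SD, and +7 to +9 at 2.0 per SD. These figures rest on the survival and censoring assumptions in step 2 of the working and on IL-8 effects that the documents do not state.

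Two stronger readings are not supported. One is that the trial cannot show whether benefit tracks IL-8: the serum is collected and the SAP is open, so an analysis can be specified, and the main limit is 50 patients. The other is that IL-8 is known for everyone before treatment: section 7.2.4 allows later batched assay, so only the draw is certain to precede treatment. For the same reason, adjustment at analysis is more practicable than stratified randomisation.

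**What to change.** Keep the ORR test and the log rank as planned. Before database lock, add to section 10.4.3 a Cox model for PFS and for OS with treatment and continuous log-transformed screening IL-8, and name its treatment HR, described as conditional, as the reported HR. This also supplies the model missing behind the HRs promised in section 10.5.

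Optionally:
- in section 10.4.2, add a supportive ORR difference standardised for screening IL-8;
- add one exploratory treatment-by-IL-8 estimate with a confidence interval, labelled as estimation only because interaction power is about 19% to 41% for 2- to 3-fold ratios of HRs.

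The cost is SAP wording. No new samples or visits are needed, and section 7.2.4 reports specimen analysis complete as of February 2024. The downsides are one extra model term, a slight loss of power if IL-8 is not prognostic, and an HR that is conditional rather than marginal.

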#### 10.4.4 Safety Analyses

Descriptive statistics will be provided for every safety endpoints by the studied arms. The occurence of safety endpoints will be compared between BMS-986253 in combination with Nivolumab in comparison to Nivolumab monotherapy.

The first six patients assigned in each arm will be monitored for AEs meeting DLT criteria as specified in Section 5. Dose Limiting Toxicities will be defined by toxicity occurring during the first 4 weeks of treatment on this study. If no treatment related AE is observed in >=4 of 6 patients, the study will continue as planned. If >2 out of 6 patients are observed to have treatment related AE (i.e., AE with no clear alternative explanation) meeting DLT criteria that has not been observed in the use of nivolumab monotherapy as described in the package insert, then a lower dose strategy for BMS-986253 (1200 mg IV q 2 weeks) vs. discontinuation of Arm 2 will be implemented in coordination with the DSMC and the study supporter.

